Participants will be randomly assigned to one of these three arms at the end of Research Visit 1 following informed consent, and data will be collected and compared at baseline and Research Visits at 6, 12, 24, and 36 months. For the group-based interventions, dietitians will deliver the adapted Look AHEAD lifestyle intervention. The goals of the diabetes lifestyle intervention program are weight loss of 5-10% of initial body weight and increased activity levels to 175 minutes/week of moderate intensity physical activity over 6 months. The adapted Look AHEAD session materials used for the pilot program are culturally sensitive and have a Flesch Reading Ease score of 74.0 and a Flesch-Kincaid grade level of 5.3. We will have Spanish versions (previously used in Look AHEAD) of all session materials available for those who prefer to read in Spanish. Materials do not focus on foods specific to individual cultures but rather build skills that participants apply to their food preferences. Accomplishment of these goals is expected to lead to improvements in weight, HbA1c, blood pressure, and lipid levels and reductions in medications used to treat these conditions.

The REAL HEALTH-Diabetes program is adapted from the published Look AHEAD program and will include 19 group sessions offered over a six-month period. The first 14 sessions will be delivered weekly and the next 5 sessions biweekly. In the subsequent 18 months,

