This program is distinct from currently available diabetes group courses based in many of the primary care practices because it focuses on developing skills for weight loss and increased activity as a means to improve glycemic control. The ultimate goal is to translate this program for delivery within the current diabetes self-management education (DSME) group course framework and, ultimately, within the context of an accountable care organization, either in person or by phone to increase reach.

A trained member of the study staff will provide MNT referral participants with an educational handout [see “11. Educational handout”] emphasizing that modest weight loss (5 – 10%) via caloric restriction and gradual adoption of moderate increases in daily physical activity (equivalent to brisk walking for 30 minutes daily) is safe and effective in managing diabetes and schedule them for an appointment with a dietitian from Nutrition Services for follow up. As per usual care procedures, Nutrition Services will bill each participant’s health insurer for dietitian services received and participants assigned to usual care will be responsible for the payment of any deductibles and co-payments required by their insurer for this routine care.

If participants have any questions about costs, we will arrange for them to speak with the study doctors and study staff and if necessary someone in Patient Financial Services about these costs.

V. STUDY PROCEDURES

For the structured interview, trained study staff will interview the respondent over the telephone to obtain feedback on the design of the telephone intervention after obtaining verbal

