Participants will then be randomly assigned to either dietitian referral for medical nutrition therapy (MNT) or the in-person or telephone group lifestyle intervention program and be assigned study ID numbers. After randomization, participants will be given a scale to self-monitor their weights. Those who are randomly assigned to the MNT arm will receive an educational handout to emphasize that modest weight loss (5 – 10%) via caloric restriction and gradual adoption of moderate increases in daily physical activity (equivalent to brisk walking for 30 minutes daily) is safe and effective in managing diabetes. They will then be referred to Nutrition Services for follow up and be given an appointment card with the time, date and location of their first Nutrition Service appointment.

Participants assigned to one of the group lifestyle intervention arms will receive information about the dates, times and location so that they can plan their attendance at the program [see “15. Look AHEAD’s group lifestyle intervention materials]. Upon completion of the visit, participants will have their parking validated, if applicable, or transportation costs reimbursed.

Participants assigned to the telephone conference call arm receive a binder of materials. The binder will contain

1. Directions for accessing the telephone conference call;
2. Handout on recognition and management of hypoglycemia (see safety monitoring);
3. Handout on monitoring blood pressure with weight loss (see safety monitoring);
4. The program materials for sessions 1-19.

The structured interviews will inform the design of the group conference call format.

Survey instruments: Patients will complete survey instruments on their own on paper or via RedCap web interface at the clinic or from a remote location. The instruments will evaluate health behaviors, self-efficacy, measures of self-determination, depression, literacy and numeracy, food insecurity, health-related quality-of-life and patient satisfaction with quality of care [see “14. Baseline and Follow-up Questionnaires]. Instruments that have validated Spanish versions will be administered in Spanish. Study staff will be available to assist with translation of untranslated instruments and with completion for participants of low literacy or with visual impairment that prevents self-completion.

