Blood Samples: Blood samples will be obtained to measure HbA1c and fasting lipids, tests that are required in usual care of people with type 2 diabetes. They will be obtained by health center phlebotomists at the health center clinical laboratory. Participants and providers will be notified that these will be obtained and billed to participants’ insurance at each research visit (0, 6, 12, 24, and 36 months), since this schedule is less than the recommended frequency for obtaining these results in usual care. Drawing them through the usual channels allows automatic entry into internal tracking systems and reduces workload on practices that may otherwise need to track patients down to meet internal performance framework reporting metrics. Data may be abstracted from clinical visits if that participant is unable to complete fasting labs at a research visit. Any missing data (second blood pressure, second weight, lipid panel) abstracted from clinical data will not be considered a deviation. Participants who are unable to complete their outcome visit in-person due to COVID-19 will have the option to email a picture of their weight, showing their feet on the scale. Participants will use send secure email unless it is documented that they opted out of send secure email at RV1. Instructions on how to measure weight will be sent to participants. For participants who have opted out of email communication, data will be

abstracted from a clinical visit as described above. The self-reported weights will be analyzed separately with sensitivity analyses. This alternative process for collecting weight data will not be considered a deviation.

Blood pressure and weight will be measured and entered by study staff into coded fields in the electronic medical record. This, too, reflects the integration of the program into usual care, and facilitates tracking of these metrics for internal performance framework reporting.

All clinical data will additionally be entered into study databases using RedCap. Survey instrument responses will be entered into RedCap.

2. Research Visits (RV2, 3, 4 and 5).

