Research Visits 2-5 will last about 2 hours. Participants will be scheduled for a research visit 6, 12, 24, and 36 months after the initiation of the intervention with a \pm 2 month visit window. Any clinical data or questionnaires that may be collected outside of the window will count for the closest visit window, with the date of data collection documented. The visit may coincide with a usual care appointment. They will receive an appointment reminder letter [see “16. RV2 Appointment Reminder Intervention and Usual Care”]. Participants will need to fast from midnight until the morning of the visit and wait until after their blood samples are drawn to take any diabetes medications. The participants will be met by a member of the study team at their health center. Participants will be asked to provide a blood sample of 6 cc taken by trained phlebotomist in the health center clinical laboratory. Subject’s blood pressure will be taken resting and will be measured in duplicate using an automated device. Height and weight will be measured and then entered into the electronic medical record to derive BMI values. Once blood samples, blood pressure and height and weight are taken and processed as outlined above, participants may take their diabetes medication(s) and will be provided a nutrition bar. Then they will be asked to complete self-administered study questionnaires on paper or via RedCap as outlined above. Any changes in medication doses for glycemic control, blood pressure and lipid management will be reviewed and confirmed by cross checking in electronic medical record.

Research visits will be conducted by a health center medical assistant, RN, or LPN who has received CITI certification in Human Subjects research and has been trained and will be funded by the REAL HEALTH-Diabetes study for this purpose. Central study personnel will support health center staff in training and assessment. Health center staff will also be supervised by the health center-based clinician co-investigators.

Participant compensation. Study participants will receive payment of \$25 for completing follow up assessments at 6 months and 1 year, \$50 at 2 years, and \$100 at 3 years to promote retention for outcome assessment.

Study outcomes/ data to be collected

AIM 1 Outcomes and Assessment Protocol

Measures at baseline and follow up assessments

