Participants will be given a calendar to track health service utilization with a particular focus on emergency room visits and hospital admissions outside the Partners system, as these cannot be tracked administratively [See “19. Medication and Health Service Utilization”]. Participants will receive postcard reminders at 3 months to remind them to keep their health service utilization calendar record.

VI. BIOSTATISTICAL ANALYSIS

a. Specific data variables (e.g. data collection sheets)

A list of the variables collected via medical chart review, survey instruments (from screening interview, research visits, RE-AIM components, and cost estimates) are listed in the protocol appendix [see “20. Data variables list”]

b. Study outcomes

All outcomes will be assessed at baseline (prior to randomization) and at 6, 12, 24 and 36 month follow up after completion of the lifestyle intervention program. Primary study endpoint will be change in weight from 0 to 6 months after enrollment in the intervention, with secondary outcomes being weight change at other timepoints, glycemia (HbA1c), blood pressure, and lipids and medication prescriptions (number, dose and cost) for these conditions as well as health behavior, self-efficacy, measures of self-determination, depression, food insecurity, health related quality-of-life, patient satisfaction, and cost.

c. Statistical methods

For all continuous outcomes (% weight loss, HbA1c, blood pressure, fasting lipid levels, self-efficacy, health related quality-of-life score, and satisfaction with care), we will compare changes from baseline among groups using a mixed effects model that includes group, follow-up period (6 months, 1 year, 2 years, 3 years), group and period interaction, baseline weight, and community health center. The follow-up period will be modeled as a categorical variable;

average changes at each time point by treatment group as well as the overall change (with all follow-up visits included in the model) will be presented. Since outcomes from participants within the same counseling group might be correlated, all analyses will take into account the clustering effect in the mixed effect models. With three treatment groups, multiple comparisons adjustment will be applied to reduce the inflation of type I error rate. Randomization codes will be generated for each health center and group assignment will occur in a 1:1:1 ratio within each site stratified by sex.

d. Power analysis

Aim 1:

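### Does the undefined start of the six-month clock in the MNT arm bias the primary weight comparison?

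*Combined protocol and SAP*

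**What the plan says.** Three statements bear on when month 6 falls.

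- Section VI.b, primary endpoint: "Primary study endpoint will be change in weight from 0 to 6 months after enrollment in the intervention".
- Section V.2, visit scheduling, with a window of plus or minus 2 months: "Participants will be scheduled for a research visit 6, 12, 24, and 36 months after the initiation of the intervention".
- Section VI.b, the sentence before the endpoint, counts follow-up from the end of the lifestyle programme.

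The origin is common to all arms. Section IV.c states: "Participants will be randomly assigned to one of these three arms at the end of Research Visit 1 following informed consent". Baseline weight is taken at that visit, before randomisation. Section V.1 (Blood Samples) places draws "at each research visit (0, 6, 12, 24, and 36 months" and makes no distinction by arm. Table 2 likewise heads the RV1 column as month 0.

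After randomisation the arms start differently (section V.1). For MNT: "Those who are randomly assigned to the MNT arm will receive an educational handout". These participants are then referred and will "be given an appointment card with the time, date and location of their first Nutrition Service appointment". Lifestyle participants "will receive information about the dates, times and location so that they can plan their attendance at the program". No maximum wait is given for any arm. The model in section VI.c treats follow-up period as a category and states no adjustment for elapsed time.

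**The concern.** The start of the intervention has a natural meaning in the two lifestyle arms, namely the first group session. In MNT it could be the handout and referral at RV1, the appointment on the card, or the first visit attended. The last may never happen, since this is billed usual care and "participants assigned to usual care will be responsible for the payment of any deductibles and co-payments".

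Suppose a coordinator uses RV1 for MNT and the first session for the lifestyle arms. The month-6 weight is then taken 6 months after baseline in MNT and 6 months plus the wait after baseline in the lifestyle arms. An MNT participant who waits for an appointment also has less than 6 months of dietitian care by then. The primary contrast would move towards the lifestyle arms even if the programmes were equally effective, and a categorical period term cannot correct for that.

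**Working it through.** **The plan's own figure.** Section VI.d uses a difference of 3.5, SD 5.5, two-sided alpha 0.05/3 = 0.0167 and 80% power, and gives 54 effective participants per arm. The normal approximation gives 52; the t-based calculation gives 53.2, rounded up to 54. The figure reproduces. Visit timing does not enter it.

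**Inputs.** Pilot six-month loss (section VI.d) is 6.7% with lifestyle, 4.1 points more than MNT, so MNT is 6.7 − 4.1 = 2.6%. As linear rates:

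- lifestyle: 6.7/6 = 1.117 points per month
- MNT: 2.6/6 = 0.433 points per month
- difference: 4.1/6 = 0.683 points per month

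The wait w from RV1 to first scheduled contact is not in the documents; 0.5, 1 and 2 months are assumed.

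**Case A: equal waits, no loss before first contact.**

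- Start-based clock in all arms: 0.683 × 6 = 4.10.
- RV1 clock in all arms: 0.683 × (6 − w).
- Split clock (MNT from RV1, lifestyle from first session): 6.7 − 0.433 × (6 − w).

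| w (months) | Start clock, all arms | RV1 clock, all arms | Split clock | Split minus start clock (0.433w) |
|---|---|---|---|---|
| 0.5 | 4.10 | 3.76 | 4.32 | 0.22 |
| 1 | 4.10 | 3.42 | 4.53 | 0.43 |
| 2 | 4.10 | 2.73 | 4.97 | 0.87 |

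The last column isolates the MNT date, because the lifestyle arms are timed from the first session in both readings. It is 6%, 12% and 25% of 3.5. The gap between the split clock and the RV1 clock is larger (1.117w = 0.56, 1.12, 2.23), but MNT is timed from RV1 in both. That gap therefore measures the choice of lifestyle clock, not the MNT ambiguity.

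**Case B: MNT loss starts at RV1 with the handout and referral; lifestyle loss starts at the first session.** Under the split clock each arm has 6 treated months. The difference is 6.7 − 2.6 = 4.10 and the shift is zero at every w.

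**Power under the two common clocks.** SE = 5.5 × √(2/54) = 1.058 and the critical value is 2.394. The start clock (4.10) gives 0.93. The RV1 clock gives 0.88, 0.80 and 0.57 in case A. In case B its differences are 6.7 × (6 − w)/6 − 2.6 = 3.54, 2.98 and 1.87, with power 0.83, 0.66 and 0.26. An RV1 clock gives up lifestyle exposure when waits are long, but it compares the arms at equal time since randomisation.

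**Does the text create the split?** Section V.2 states one rule for all participants. Section V.1 places study enrolment at RV1 for everyone, and the month-0 labels in section V.1 and Table 2 are not arm-specific. The split appears only if one phrase is read in two ways.

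**The end-of-programme clause.** The intensive phase is 14 weekly plus 5 biweekly sessions: 14 + 10 = 24 weeks, about 5.5 months. Monthly sessions then run to month 24. Six months after completion would be about month 11.5 or month 30, and neither fits the endpoint sentence that follows or the visit schedule. It is a drafting slip.

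**The case for a change.** The strongest case for a change is that this is the primary endpoint, the arms really do start by different routes, and section V.2, which sets the visit dates, names an event other than RV1. The month-0 labels do not define that event. If the programmes were equally effective, the split clock under case A would raise the per-comparison error rate from 0.0167 to 0.019, 0.026 or 0.058 for waits of 0.5, 1 or 2 months. One sentence would close the gap.

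What stands is that the wording is loose and that one sentence would tidy it. The error rates do not show a fault in the plan. They need staff to apply one rule differently by arm, a wait that no document gives, and no MNT weight loss before the appointment, although the handout, the referral and a scale for self-weighing are all provided at RV1. The comparator is also described throughout as referral to MNT, the current standard of care. In a translational trial, the wait for an appointment is arguably part of that policy, so shorter dietitian exposure is not automatically bias.

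Nor is there one obviously better definition. A start-based clock keeps the month-6 visit just after the 24-week intensive phase, but it lets time since the RV1 baseline differ by arm if waits differ. An RV1 clock equalises that interval but can cost power. Either is defensible if used in every arm.

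**Conclusion.** The concern identifies a real ambiguity but not a defect that calls for a change. The plan words the time origin in more than one way and does not define it by arm. It nowhere assigns different clocks to different arms, and a team applying section V.2 uniformly gets a sound comparison under either reading.

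If the clocks were split, the shift would be 0.22 to 0.87 points for waits of 0.5 to 2 months under case A, and zero under case B. Both cases assume linear loss at pilot rates and no lifestyle loss before the first session. If lifestyle participants also lost weight while waiting, the split would favour them somewhat more. The documents show neither the size nor the direction of any actual bias.

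Baseline is fixed at RV1, and section V.2 requires dates to be documented for data collected outside the window. An analyst can tabulate the RV1-to-month-6 interval by arm as ordinary reporting, which would reveal a split. The sample size of 210 does not depend on the point.

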Sample size/power calculation.

H1a. IDOLc preliminary data showed 6.7% mean weight loss at 6 months in the lifestyle intervention group, which was 4.1% greater than the MNT group. The standard deviation of percent weight loss in the pilot cohort was 5.5. Our aim is to detect a clinically meaningful 3.5% difference between any of the two study groups (where weight maintenance is defined as weight change <3%⁷¹). We use the conservative Bonferroni method to adjust for 3-arm multiple comparisons, which reduces the two-sided significance level to 0.0167 (0.05/3). Assuming a SD of 5.5%, the study will need an effective sample size of 54 per arm to detect a 3.5% difference with 80% power. We assume a conservative intraclass correlation coefficient of 0.02 within each counseling group, which translates into an inflation factor of 1.2, and 10% drop-out rate based on our prior results and the fact that participants receive primary care at study sites. The final sample size will be 210, 70 per arm.

Further analyses:

H1b. We hypothesize that participants in the group interventions will maintain or improve HbA1c, blood pressure, and LDL with reduced medication use (dose and cost) to treat these conditions, both at the end of the intensive intervention and at follow-up, compared to the MNT arm. Medication reduction is an outcome that is meaningful to participants and reduces costs to payors (40,41). Based on our preliminary data, in which 61% of the lifestyle group had improved HbA1c on less medication compared to 31% in the MNT group, we have 81% power to detect a difference of 33% with an effective sample size of 54 per group, adjusting for the 3-arm comparison. We will perform further analyses employing number of medications, insulin use, insulin doses, and Diabetes Medication System Questionnaire, PAM-D or similar weights to model differences in medication intensity among groups (42,43).

H1c. Using the standard deviation estimates from our previous data (44,45), the study will have 80% power to detect a mean difference of 0.35 (on a scale of 1 to 5) in the change of low-fat diet self-efficacy measure between the two lifestyle change arms or between either lifestyle change and the MNT arm, assuming a standard deviation of 0.55. For the change in exercise self-efficacy measure, the study will have 80% power to detect a mean difference of 0.88 (on a scale of 1 to 7), respectively, assuming a standard deviation of 1.4.

Aim 2:

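### The VI.c mixed model leaves the secondary continuous outcomes unadjusted for their own baseline and omits sex, a randomisation stratum; adding both is a nearly free gain in precision

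*Combined protocol and SAP*

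**What the plan says.** Section VI.c (Statistical methods) gives a single model for percent weight loss, HbA1c, blood pressure, lipids, self-efficacy, quality of life and satisfaction with care: "we will compare changes from baseline among groups using a mixed effects model". The fixed terms are group, follow-up period, and "group and period interaction, baseline weight, and community health center". On time, "The follow-up period will be modeled as a categorical variable", and the plan will report "average changes at each time point by treatment group as well as the overall change". Clustering by counselling group is to be taken into account.

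The same section says that "group assignment will occur in a 1:1:1 ratio within each site stratified by sex". Health center is therefore both a stratum and a model term, while sex is a stratum only. No other section adds an own-baseline covariate or sex.

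Section VI.b schedules outcome assessment before randomisation, so the baseline values will be available. Section VI.d (H1c) claims "80% power to detect a mean difference of 0.35 (on a scale of 1 to 5) in the change of low-fat diet self-efficacy measure", with an SD of 0.55, and makes a similar claim for exercise self-efficacy (difference 0.88, SD 1.4).

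**The concern.** A change score subtracts the baseline with a fixed slope of 1. That is efficient only when the regression of follow-up on baseline really has slope 1. Otherwise, fitting the slope removes more variance at almost no cost. For percent weight loss, baseline weight already does this. For the other outcomes, baseline weight is a different variable and is no substitute for their own baseline.

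What is at stake is power for the H1b and H1c continuous outcomes. H1c is planned at barely 80%. In the pilot, HbA1c improved by 0.70 against 0.39, a difference of 0.31 points with P = 0.38, so precision for HbA1c matters too. Omitting a stratification factor makes tests at most slightly conservative. That part is small, but it also touches the primary outcome.

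The point is confined to this model. VI.c gives no covariate model for the H1b proportion, the medication outcomes or cost.

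**Working it through.** **Inputs.** From VI.d: two-sided alpha 0.05/3 = 0.0167; effective n = 54 per arm; primary difference 3.5 with SD 5.5; diet self-efficacy 0.35 with SD 0.55; exercise self-efficacy 0.88 with SD 1.4. From the pilot results in the background: HbA1c change SDs 1.13 and 1.51. Assumed, because the documents do not give them: rho, the baseline to follow-up correlation, and k, the baseline SD divided by the follow-up SD.

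**Step 1: the plan's own figures.** The two-sample noncentral t at 54 per arm gives 80.7% for the primary outcome, 80.7% for diet and 79.6% for exercise. All three reproduce the stated 80%.

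**Step 2: variance with and without own baseline, one visit.** Set the follow-up SD to 1.

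- Change score: 1 + k² − 2·rho·k
- Own baseline fitted: 1 − rho²
- Difference: (k − rho)², which is never negative and is nil when rho = k

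Multiplying each SD of change by the square root of the variance ratio gives:

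| k | rho | variance ratio | SE reduction | diet power | exercise power |
|---|---|---|---|---|---|
| 1 | 0.3 | 0.650 | 19% | 95.1% | 94.5% |
| 1 | 0.5 | 0.750 | 13% | 91.5% | 90.8% |
| 1 | 0.7 | 0.850 | 8% | 87.4% | 86.4% |
| 0.8 | 0.3 | 0.784 | 11% | 90.1% | 89.3% |
| 0.8 | 0.5 | 0.893 | 5.5% | 85.5% | 84.5% |
| 0.8 | 0.7 | 0.981 | 1% | 81.6% | 80.5% |

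A simulation (4,000 replicates, k = 1, rho = 0.5, diet figures) confirms that baseline weight does not do this work. Power was 80.5% to 81.2% for change alone, 79.8% to 81.2% with baseline weight added, and 91.4% to 91.6% with own baseline added.

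**Step 3: HbA1c.** The pooled pilot SD of change is sqrt((1.13² + 1.51²)/2) = 1.33. The difference detectable with 80% power is 0.84 points as planned. With own baseline, at rho 0.3/0.5/0.7, it becomes 0.68/0.73/0.78 (k = 1) or 0.75/0.80/0.83 (k = 0.8).

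**Step 4: why the baseline term needs its own slope at each visit.** Results are reported by visit, and rho usually falls with time. Take k = 0.8 and rho = 0.8, 0.7, 0.6, 0.5 at 6, 12, 24 and 36 months (assumed). A common slope that weights visits equally has b = mean(rho)/k, so b·k = 0.65, and the variance at each visit is 1 + 0.65² − 2·0.65·rho.

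| Month | change score | common slope | separate slopes | SE, common | SE, separate |
|---|---|---|---|---|---|
| 6 | 0.360 | 0.383 | 0.360 | +3.1% | 0 |
| 12 | 0.520 | 0.513 | 0.510 | −0.7% | −1.0% |
| 24 | 0.680 | 0.643 | 0.640 | −2.8% | −3.0% |
| 36 | 0.840 | 0.773 | 0.750 | −4.1% | −5.5% |

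A common slope can lose precision at a visit; separate slopes do not, apart from degrees of freedom.

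**Step 5: sex.** If sex explains a share R² of the variance, the residual SD is 5.5·sqrt(1 − R²). Primary power goes from 80.7% to 81.2% (R² = 1%) or 83.0% (R² = 5%). By the normal approximation, leaving sex out makes the nominal 0.0167 test run at about 0.0161 or 0.0140.

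**Step 6: cost of the terms.** When rho = k, estimating a slope costs sqrt(1 + 1/157) − 1 = 0.3% of the standard error with three arms of 54. Five fewer degrees of freedom take primary power from 80.73% to 80.66%.

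**The case against.** The strongest reply is that nothing in the plan is wrong. A change-score mixed model is valid, the primary outcome already carries its own baseline, and H1c reaches its stated power. That stands, so this is an improvement and not a correction.

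The size of the benefit is also uncertain. It runs from 19% of the standard error down to nothing, on quantities the documents do not supply. The eligibility limits in III.a truncate baseline HbA1c and blood pressure, which points to k below 1 for those outcomes, so the k = 1 figures probably fit them least. That stands too.

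Holding effective n at 54 favours the adjustment, because a baseline covariate may not reduce variance that arises in the counselling groups after randomisation. Suppose the cluster variance stays at 2% of the change variance, with groups of 10. Effective n is then 54·1.18/(1 + 0.18/ratio), or about 50/51/53 at k = 1, and diet power is 93/90/86% instead of 95/92/87%. At k = 0.8 it is 89/85/81% instead of 90/86/82%. The powers in the table are best read as upper values; the direction does not change.

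The common-slope figures depend on how visits are weighted, and VI.c names no within-person covariance. They illustrate why separate slopes are preferable and are not predictions.

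Finally, the authors may have meant each outcome's own baseline and written the weight version as a template. The text does not say so. If that was the intent, the fix merely records it.

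**Conclusion.** The point holds. As written, VI.c fits the non-weight continuous outcomes without their own baseline and all outcomes without sex. The consequence is lost precision, with no bias, no inflated type I error, and no effect on the sample size of 210 or the powered H1b proportion.

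For rho between 0.3 and 0.7, the single-visit saving in standard error is 8% to 19% if k = 1 and 1% to 11% if k = 0.8, and nil if rho = k. These ranges rest on assumed rho and k. The power figures also take 0.55 and 1.4 as SDs of change, which is the natural reading of H1c, and hold effective n at 54. For HbA1c, adjustment narrows but does not close the distance between the detectable difference and the 0.31 points seen in the pilot. The sex term matters little, at 0.5 to 2.3 points of primary power on the assumed R² values. Because the downside is about 0.3% of a standard error, the change should be made.

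**What to change.** In VI.c, keep baseline weight and health center. For continuous outcomes other than weight, add *the baseline value of the outcome being analysed, where measured at baseline, and its interaction with follow-up period*. Add sex as a fixed effect for every outcome in this model. Fix this wording before the outcome data are analysed, so that the covariates are not chosen afterwards.

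Instruments not given at baseline in Table 2 (Program Satisfaction and, if it is analysed with this model, the Health Care Climate Questionnaire) cannot take the own-baseline term. It would also help to state in VI.d whether 0.55 and 1.4 are SDs of change or of the score.

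The cost is one sentence and a few degrees of freedom. Sex is known at randomisation and the baseline values are already scheduled, so no participants, visits or measurements are added.
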